10.2. Appendix 2: Clinical Laboratory Tests

The following tests will be performed according to the [Schedule of Activities](#) by the selected laboratory. The tests to be performed are discussed in Section 8.2.4 of the Master Protocol PLATFORMPAHPB2001.

Below is the list of protocol-required safety laboratory assessments that will be evaluated in this study. The additional assessments specific for this ISA are highlighted (colored fill).

Protocol-Required Safety Laboratory Assessments

Laboratory Assessments	Parameters		
Hematology	Platelet count Red blood cell count Hemoglobin Hematocrit	RBC Indices: MCV MCH % Reticulocytes	White Blood Cell (WBC) count with Differential: Neutrophils Lymphocytes Monocytes Eosinophils Basophils
	Note: A WBC evaluation may include any abnormal cells, which will then be reported by the laboratory. An RBC evaluation may include abnormalities in the RBC count, RBC parameters, or RBC morphology, which will then be reported by the laboratory. In addition, any other abnormal cells in a blood smear will also be reported.		
Clinical Chemistry	Sodium Potassium Chloride Bicarbonate Blood urea nitrogen (BUN) Creatinine Cystatin C Glucose Aspartate aminotransferase (AST) Alanine aminotransferase (ALT) Gamma-glutamyltransferase (GGT) α_1 -acid glycoprotein Fibrinogen (on blood) eGFR calculation based on Creatinine (eGFR _{cr} ; by CKD EPI formula) eGFR calculation based on Cystatin C (eGFR _{cys} ; by CKD EPI formula)	Total, direct, indirect bilirubin Alkaline phosphatase Creatine phosphokinase (CPK) Lactic acid dehydrogenase (LDH) Uric acid Calcium Phosphate Albumin Total protein Total cholesterol High-density lipoprotein cholesterol Low-density lipoprotein cholesterol Triglycerides Magnesium Lipase Amylase (reflex testing of pancreatic amylase should be done in case of amylase or lipase increase from screening onwards)	

Laboratory Assessments	Parameters	
Routine Urinalysis	Dipstick Specific gravity pH Glucose Protein Blood Ketones Bilirubin Urobilinogen Nitrite Leukocyte esterase	Sediment (if dipstick result is abnormal) Red blood cells White blood cells Epithelial cells Crystals Casts Bacteria
	In case of a positive dipstick result, a urine sample will be set aside for additional examination of the positive parameter (eg, quantification as applicable).	
Urine Chemistry (quantitative measurement)	Creatinine Sodium Phosphate	Glucose Protein Albumin
Renal Biomarkers	Retinol binding protein ^a Beta-2-microglobulin ^a Note: Other biomarkers might be measured.	
Other Tests	
 • At screening, a follicle-stimulating hormone (FSH) test will be performed for postmenopausal women (see Section 10.5, Appendix 5). • At screening, a HIV-1 and -2 test, and hepatitis A, B, C, D, and E tests will be performed. • At screening, hemoglobin A1c will be measured. • At screening and time points as indicated in the Schedule of Activities, alpha-fetoprotein (AFP) will be measured. • At screening and time points as indicated in the Schedule of Activities, tests for coagulation parameters will be performed. The international normalized ratio (INR) will be calculated by the central laboratory. • At screening serum pregnancy testing will be done for women of childbearing potential only. • At baseline (Day 1) and time points as indicated in the Schedule of Activities, a urine pregnancy test will be performed for women of childbearing potential only. • Testing for HBsAg, HBeAg, and anti-HBs, anti-HBc and anti-HBe antibodies at the time points indicated in the Schedule of Activities. • Thyroid function tests (TSH and T4) will be performed at screening and time points indicated in the Schedule of Activities. • Optional tests in response to ALT flare (refer to Section 10.7, Appendix 7): 
 ○ Testing for HIV-1 and -2, and hepatitis A, C, D, and E ○ Testing for CMV, HSV, EBV infection ○ Ig-Electrophoresis ○ AFP sampling 	

^a Retinol binding protein and beta-2-microglobulin need to be assessed based on the same urine sample.

10.3. Appendix 3: Regulatory, Ethical, and Study Oversight Considerations

10.3.1. Regulatory and Ethical Considerations

Refer to Attachment 3 of the Master Protocol PLATFORMPAHPB2001.

10.3.2. Financial Disclosure

Refer to Attachment 3 of the Master Protocol PLATFORMPAHPB2001.

10.3.3. Informed Consent Process

Refer to Attachment 3 of the Master Protocol PLATFORMPAHPB2001.

10.3.4. Data Protection

Refer to Attachment 3 of the Master Protocol PLATFORMPAHPB2001.

10.3.5. Long-Term Retention of Samples for Additional Future Research

Refer to Attachment 3 of the Master Protocol PLATFORMPAHPB2001.

10.3.6. Committees Structure

Data Review Committee

The internal DRC established for the Platform study will review interim data and formulate recommendations to protect the safety and well-being of the participants. Description of the DRC is provided in Section 9.6 of the Master Protocol PLATFORMPAHPB2001. The possible recommendations and role of the DRC will be further detailed in the DRC charter for this ISA.

Independent Flare Expert Panel

An IFLEP will be appointed. The IFLEP is composed of 3 independent medical experts with experience and expertise in HBV and its treatment. The IFLEP will monitor ALT flares and will make recommendations regarding flare management based on an analysis of aggregate data.

In order to allow for an unbiased assessment, members of the committee will not serve as study investigators or as members of the DRC.

Further details on the IFLEP process will be included in the IFLEP charter.

10.3.7. Publication Policy/Dissemination of Clinical Study Data

Refer to Attachment 3 of the Master Protocol PLATFORMPAHPB2001.

10.3.8. Data Quality Assurance

Refer to Attachment 3 of the Master Protocol PLATFORMPAHPB2001.

10.3.9. Case Report Form Completion

Refer to Attachment 3 of the Master Protocol PLATFORMPAHPB2001.

10.3.10. Source Documents

Refer to Attachment 3 of the Master Protocol PLATFORMPAHPB2001.

10.3.11. Monitoring

Refer to Attachment 3 of the Master Protocol PLATFORMPAHPB2001.

10.3.12. On-Site Audits

Refer to Attachment 3 of the Master Protocol PLATFORMPAHPB2001.

10.3.13. Record Retention

Refer to Attachment 3 of the Master Protocol PLATFORMPAHPB2001.

10.3.14. Study and Site Start and Closure

Refer to Attachment 3 of the Master Protocol PLATFORMPAHPB2001.

10.4. Appendix 4: Adverse Events, Serious Adverse Events, Product Quality Complaints, and Other Safety Reporting: Definitions and Procedures for Recording, Evaluating, Follow-up, and Reporting**10.4.1. Adverse Event Definitions and Classifications**

Refer to Attachment 4 of the Master Protocol PLATFORMPAHPB2001.

10.4.2. Attribution Definitions

Refer to Attachment 4 of the Master Protocol PLATFORMPAHPB2001.

10.4.3. Severity Criteria

Refer to Attachment 4 of the Master Protocol PLATFORMPAHPB2001.

10.4.4. Special Reporting Situations

Refer to Attachment 4 of the Master Protocol PLATFORMPAHPB2001.

10.4.5. Procedures

Refer to Attachment 4 of the Master Protocol PLATFORMPAHPB2001.

10.4.6. Product Quality Complaint Handling

Refer to Attachment 4 of the Master Protocol PLATFORMPAHPB2001.

10.4.7. Contacting Sponsor Regarding Safety, Including Product Quality

Refer to Attachment 4 of the Master Protocol PLATFORMPAHPB2001.

10.5. Appendix 5: Contraceptive and Barrier Guidance

Participants must follow contraceptive measures as outlined in Section 5.1. Pregnancy information will be collected and reported as noted in Section 8.3.5.

Definitions

Woman of Childbearing Potential (WOCBP)

A woman is considered fertile following menarche and until becoming postmenopausal unless permanently sterile (see below).

Woman Not of Childbearing Potential

- **premenarchal**
A premenarchal state is one in which menarche has not yet occurred.
- **postmenopausal**
A postmenopausal state is defined as no menses for 12 months without an alternative medical cause. A high follicle-stimulating hormone (FSH) level (>40 IU/L or mIU/mL) in the postmenopausal range may be used to confirm a postmenopausal state in women not using hormonal contraception or hormonal replacement therapy (HRT). However, in the absence of 12 months of amenorrhea, a single FSH measurement is insufficient to confirm a woman is not of childbearing potential. If there is a question about menopausal status in women on HRT, the woman will be required to use one of the non-estrogen-containing hormonal highly effective contraceptive methods if she wishes to continue HRT during the study.
- **permanently sterile**
Permanent sterilization methods include hysterectomy, bilateral salpingectomy, or bilateral oophorectomy.

Note: If the childbearing potential changes after start of the study (eg, a premenarchal woman experiences menarche) or the risk of pregnancy changes (eg, a woman who is not heterosexually active becomes active), a woman must begin a highly effective method of contraception, as described throughout the inclusion criteria.

If reproductive status is questionable, additional evaluation should be considered.

Contraceptive (birth control) use by men or women should be consistent with local regulations regarding the acceptable methods of contraception for those participating in clinical studies.

Examples of Contraceptives

EXAMPLES OF CONTRACEPTIVES^a ALLOWED DURING THE STUDY INCLUDE:
USER INDEPENDENT
Highly Effective Methods That Are User Independent Failure rate of <1% per year when used consistently and correctly.

 • Implantable progestogen-only hormone contraception associated with inhibition of ovulation • Intrauterine device (IUD) • Intrauterine hormone-releasing system (IUS) • Tubal closure (eg, bilateral tubal occlusion, bilateral tubal ligation)

- Azoospermic partner (*vasectomized or due to medical cause*)
(Vasectomized partner is a highly effective contraceptive method provided that the partner is the sole sexual partner of the woman of childbearing potential and the absence of sperm has been confirmed. If not, additional highly effective method of contraception should be used. Spermatogenesis cycle is approximately 74 days.)

USER DEPENDENT

Highly Effective Methods That Are User Dependent *Failure rate of <1% per year when used consistently and correctly.*

- Combined (estrogen- and progestogen-containing) hormonal contraception associated with inhibition of ovulation

oral
intravaginal
transdermal
injectable

- Progestogen-only hormone contraception associated with inhibition of ovulation

oral
injectable

- Sexual abstinence

(Sexual abstinence is considered a highly effective method only if defined as refraining from heterosexual intercourse during the entire period of risk associated with the study intervention. The reliability of sexual abstinence needs to be evaluated in relation to the duration of the study and the preferred and usual lifestyle of the participant.)

- a) Typical use failure rates may differ from those when used consistently and correctly. Use should be consistent with local regulations regarding the use of contraceptive methods for participants in clinical studies.

10.6. Appendix 6: Rash Management

Table 4: Management of Rash Events by Severity Grade

	Definition	Study Intervention Action	Activities by Day^a	Referral to Dermatologist and Dermatology Activities
Grade 1 rash (with or without pruritus)^b	Erythema	Study intervention intake may be continued at the investigator's discretion	
Day 0: optional on-site visit for initial rash evaluation may be performed at the investigator's discretion.
 
Safety laboratory assessments may be performed at the investigator's discretion (recommended if visit occurs).
 
Digital pictures^c of skin lesions may be taken at the investigator's discretion.
 
Determine if participant was adhering to the recommended sun-protective measures. If appropriate, provide sun protection counseling.
 
Day 1 and thereafter: appropriate follow-up visits at the investigator's discretion until resolution of rash.
 
Safety laboratory assessments and photography (digital pictures^c of skin lesions) may be performed at the investigator's discretion.
	Not required
Grade 2 rash (with or without pruritus)^b	Diffuse, maculopapular rash, or dry desquamation	Study intervention intake may be continued at the investigator's discretion	
Day 0: required on-site visit (if a visit is not possible, telephone contact with the participant should take place to collect information and give advice on the necessary measures to be taken).
 
Safety laboratory assessments may be performed at the investigator's discretion (recommended).
 
Digital pictures^c of skin lesions may be taken at the investigator's discretion. Digital pictures^c of skin lesions are recommended in case consultation of a dermatologist is required. Determine if participant was adhering to the recommended sun-protective measures. If appropriate, provide sun protection counseling.
 
Day 1 and thereafter: appropriate follow-up visits at the investigator's discretion until resolution of rash or until clinical stability is reached.
 
Safety laboratory assessments are required on Day 1 and are required thereafter only if the previous values were abnormal (but may be
	
Referral to dermatologist at the discretion of the investigator^d
 
Biopsy not required, but may be performed at the dermatologist's discretion

Table 4: Management of Rash Events by Severity Grade

	Definition	Study Intervention Action	Activities by Day^a	Referral to Dermatologist and Dermatology Activities
			performed at the investigator's discretion). If the rash progresses to a higher grade, safety laboratory assessments of the higher grade should be followed. Digital pictures ^c of skin lesions may be taken at the investigator's discretion.	
Grade 3 rash^b	Vesiculation, moist desquamation, or ulceration OR Any cutaneous event with 1 of the following: - Elevations in AST/ALT >2×baseline value - Fever >38°C or 100°F - Eosinophils >1.00×10 ³ /μL - Serum sickness-like reaction	Must permanently discontinue JNJ-3989 and JNJ-6379 and PegIFN-α2a; no rechallenge allowed NA treatment may be discontinued based on investigator judgement in consultation with the Sponsor	Day 0 : required on-site visit. Safety laboratory assessments required to be performed. Digital pictures ^c of skin lesions may be taken at the investigator's discretion (recommended). Determine if participant was adhering to the recommended sun-protective measures. If appropriate, provide sun protection counseling. Day 1 : required on-site visit. Safety laboratory assessments required to be performed. Digital pictures ^c of skin lesions may be taken at the investigator's discretion (recommended). Further visit(s) : appropriate follow-up required until resolution of rash or until clinical stability is reached. Safety laboratory assessments and photography (digital pictures ^c of skin lesions) are recommended to be performed until the rash severity resolves to Grade 2 or Grade 1.	Required ^d Biopsy not required, but may be performed at the dermatologist's discretion.
Grade 4 rash	Exfoliative dermatitis OR Mucous membrane involvement in at least 2 distinct sites OR Erythema multiforme major OR	Must permanently discontinue JNJ-3989 and JNJ-6379 and PegIFN-α2a; no rechallenge allowed	Day 0 : required on-site visit. Safety laboratory assessments required to be performed. Digital pictures ^c of skin lesions may be taken at the investigator's discretion (recommended). Determine if participant was adhering to the recommended sun-protective measures. If appropriate, provide sun protection counseling.	Required ^d Biopsy required and to be performed as soon as possible after the onset of the rash.

Table 4: Management of Rash Events by Severity Grade

Definition	Study Intervention Action	Activities by Day ^a	Referral to Dermatologist and Dermatology Activities
Stevens-Johnson syndrome OR Toxic epidermal necrolysis OR Necrosis requiring surgery	NA treatment may be discontinued based on investigator judgement in consultation with the Sponsor	Day 1 : required on-site visit. Safety laboratory assessments required to be performed. Digital pictures ^c of skin lesions may be taken at the investigator's discretion (recommended). Further visit(s) : appropriate follow-up required until resolution of rash or until clinical stability is reached. Safety laboratory assessments and photography (digital pictures ^c of skin lesions) are recommended to be performed until the rash severity resolves to Grade 2 or Grade 1.	

[figure not shown]
AE: adverse event; ALT: alanine aminotransferase; AST: aspartate aminotransferase; NA: nucleos(t)ide analog.

- ^a Day 0 of the rash is the first day of investigator assessment and not the first day of rash as reported by the participant. The initial visit should be conducted as soon as possible after the participant contacts the investigator to report the AE (ie, preferably on Day 0). The initial visit and subsequent visits to manage the rash may require unscheduled visit(s).
- ^b The participant should be advised to contact the investigator immediately if there is any worsening of the rash, if any systemic signs or symptoms appear, or if mucosal involvement develops. In case the rash evolves to a higher grade than that first observed, management of the rash should follow the guidelines indicated for the higher grade.
- ^c Digital pictures to be taken at the clinical site upon consent of the participant.
- ^d If applicable, dermatologist visit should occur preferably within 24 hours after onset of rash.

Notes:

- Local laboratory assessments are to be used for rash management. The values of the local laboratory assessments need to be transcribed in the CRF by the study site personnel.
- A copy of the dermatologist's report, biopsy, and/or digital pictures if performed, should be made anonymous and will be provided to the sponsor.

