2.2.3.3. Combination of JNJ-3989 and PegIFN- $\alpha 2a$

PegIFN- $\alpha 2a$ is a covalent conjugate of recombinant alfa-2a interferon that is indicated for the treatment of chronic HBV infection in adult and pediatric patients at least 3 years of age. In addition, PegIFN- $\alpha 2a$ in combination with other medicinal products is indicated for the treatment of chronic hepatitis C virus (HCV)-infection in adult and pediatric patients at least 5 years of age and not treated before. The most common adverse reactions ($\geq 10\%$ of participants) are anorexia, anxiety, headache, concentration impairment, dyspnea, cough, alopecia, dermatitis, pruritis, dry skin, myalgia, arthralgia, asthenia, pyrexia, and fatigue. For further information regarding PegIFN- $\alpha 2a$, refer to the currently approved prescribing information.

Treatment with PegIFN- $\alpha 2a$ has been associated with decreases in platelet count (common adverse reaction). Of the 84 adult chronic HBV-infected participants that received 3 subcutaneous injections of JNJ-3989 in the Phase 1/2a AROHBV1001 study (see Section 2.2.3.1, JNJ-3989), 6 participants developed Grade 1 platelet reduction with no general trend towards a continuous decline.

No pharmacokinetic (PK) interaction is expected between JNJ-3989 and PegIFN- $\alpha 2a$ based on the known pharmacologic profile of JNJ-3989 (IB JNJ-3989; Yeh 2019).

At the time of protocol writing, 2 clinical studies using the combination of JNJ-3989 and PegIFN- α 2a are ongoing: REEF-IT and PENGUIN. Nonclinical studies to investigate the effect on platelet count decreases were completed and results are summarized in Section 2.2.2.1, JNJ-3989. Up to 48-week hematology data from the ongoing Phase 2 clinical study REEF-1 are available and overall around 5% of the participants experienced AEs or laboratory abnormalities related to hematologic abnormalities, the majority of mild to moderate severity. The hematologic abnormalities resolved on continued JNJ-3989+NA treatment.

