7.1. Discontinuation of Study Intervention

Treatment with JNJ-3989 (and PegIFN- α 2a if applicable) must be discontinued prematurely if any of the discontinuation criteria listed below are met. Criteria specific for this ISA are highlighted (colored fill). For the few criteria from the Master Protocol that are specified or more restricted in this ISA, the changes compared to the Master Protocol are also highlighted (colored fill). If JNJ-3989 is prematurely discontinued, PegIFN- α 2a (if applicable) should also be discontinued. If PegIFN- α 2a is prematurely discontinued (ie, before Week 23 [Arms 1 and 2] or before Week 11 [Arm 3]), treatment with JNJ-3989 and NA should be continued as planned. NA treatment may be continued or, in consultation with the Sponsor, discontinued based on investigator judgement.

The discontinuation criteria are:

- The participant withdraws consent to receive study intervention.
- The investigator believes that for safety or tolerability reasons (eg, AE) it is in the best interest of the participant to discontinue JNJ-3989 (and PegIFN- α 2a, if applicable).
- The participant becomes pregnant.
- The participant has a \geq Grade 3 rash (see Section 10.6, Appendix 6: Rash Management) or allergic reaction (see Section 8.3.7.3, Acute Systemic Allergic Reactions).
- The participant has signs of hepatic decompensation (ie, clinical evidence of ascites, bleeding varices, or hepatic encephalopathy) or an increase in direct bilirubin $>1.5\times$ ULN in combination with INR $\geq 1.5\times$ ULN or albumin <3.0 g/dL. Treatment with JNJ-3989 should be discontinued and alternative treatment options (outside the study) should be considered in discussion with the Sponsor.
- The participant has a confirmed \geq Grade 3 eGFR abnormality and a drop from baseline of >10 mL/min/ 1.73 m², considered at least possibly related to JNJ-3989 (or PegIFN- α 2a, if applicable) that persists despite changing tenofovir disoproxil to ETV or TAF (if the patient was receiving tenofovir disoproxil) (see Section 8.3.7.2, Renal Complications).
- The participant has a QTcF prolongation (defined as a QTcF value of >500 ms, or an increase from baseline of >60 ms) at any given time point.
- The participant requires ≥ 7 days of treatment with any of the disallowed medications listed in Section 6.8, Concomitant Therapy, and does not intend to discontinue treatment with the disallowed medication.

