- The participant has confirmed HBV virologic breakthrough (ie, confirmed on-treatment HBV DNA increase by >1 log₁₀ IU/mL from nadir or confirmed on-treatment HBV DNA level >200 IU/mL in participants who had HBV DNA level $<$ LLOQ of the HBV DNA assay).

If virologic breakthrough occurs during PegIFN- α 2a administration, this does not automatically lead to stop of JNJ-3989 and/or PegIFN- α 2a, but should be assessed/discussed with the Sponsor.

In case of virologic breakthrough, a viral sequencing sample will be collected during an unscheduled visit within 7 days of the DNA increase.

- The participant has ALT/AST elevations, as described in Section 8.3.6.2, Intervention-emergent ALT/AST Elevations.

Note: The grades are based on the DAIDS Toxicity Grading Scale (see Section 10.9, Appendix 9: DAIDS Table).

In addition, PegIFN- α 2a must immediately be discontinued for any of the following reasons:

- Participant has platelet count $<25,000$ cells/mm³.
- Participant has ANC <500 cells/mm³.

Note: PegIFN- α 2a treatment can be restarted when ANC values return to more than 1,000 cells/mm³ (see details in Section 6.5, Dose Modification)

- Participant develops evidence of hepatic decompensation during treatment, or ALT increase clinically significant or accompanied by direct bilirubin increase.
- Participant develops thyroid disorders or diabetes during treatment and cannot be controlled with medication.
- Participant develops new or worsening ophthalmologic disorders.
- Participant develops any deterioration of cardiovascular status.
- Participant develops serious, acute hypersensitivity reaction (eg, urticaria, angioedema, bronchoconstriction, anaphylaxis).
- Participant develops serious infection (bacterial, viral, fungal) and sepsis.
- Participant develops persistent or unexplained pulmonary infiltrates or pulmonary function impairment.
- Participant with onset or worsening of psoriatic lesion.
- Participant develops moderate or severe depression, or other psychiatric symptoms (for mild depression, treatment discontinuation may be considered).

Note: Participants who develop a neuropsychiatric AE during PegIFN- α 2a treatment, will be monitored closely until the neuropsychiatric AE resolves, with frequent (at least weekly) follow-up phone calls.

- Participant develops colitis symptoms (such as but not limited to abdominal pain, bloody diarrhea, and fever).
- Participant develops symptoms or signs suggestive of pancreatitis.

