Fatigue or Malaise Report only 1	Symptoms causing no or minimal interference with usual social & functional activities	Symptoms causing greater than minimal interference with usual social & functional activities	Symptoms causing inability to perform usual social & functional activities	Incapacitating symptoms of fatigue or malaise causing inability to perform basic self care functions
Fever (non axillary temperatures only)	38.0°C to <38.6°C or 100.4°F to <101.5°F	$\geq 38.6^\circ\text{C}$ to <39.3°C or $\geq 101.5^\circ\text{F}$ to <102.7°F	$\geq 39.3^\circ\text{C}$ to <40.0°C or $\geq 102.7^\circ\text{F}$ to <104.0°F	$\geq 40.0^\circ\text{C}$ or $\geq 104.0^\circ\text{F}$
Painⁱ (not associated with study intervention injections and not specified elsewhere) Specify location	Pain causing no or minimal interference with usual social & functional activities	Pain causing greater than minimal interference with usual social & functional activities	Pain causing inability to perform usual social & functional activities	Disabling pain causing inability to perform basic self care functions OR Hospitalization indicated
Serum Sickness^j	Mild signs and symptoms	Moderate signs and symptoms AND Intervention indicated (eg, antihistamines)	Severe signs and symptoms AND Higher level intervention indicated (eg, steroids or IV fluids)	Life threatening consequences (eg, requiring pressor or ventilator support)

IV: intravenous; NAP: not applicable

^h A disorder characterized by nausea, headache, tachycardia, hypotension, rash, and/or shortness of breath.

ⁱ For pain associated with injections or infusions, refer to SITE REACTIONS TO INJECTIONS AND INFUSIONS section.

^j A disorder characterized by fever, arthralgia, myalgia, skin eruptions, lymphadenopathy, marked discomfort, and/or dyspnea.

SYSTEMIC				
PARAMETER	GRADE 1 MILD	GRADE 2 MODERATE	GRADE 3 SEVERE	GRADE 4 POTENTIALLY LIFE- THREATENING
Underweight^k aged >5 to 19 years	WHO BMI z score < 1 to 2	WHO BMI z score < 2 to 3	WHO BMI z score < 3	WHO BMI z score < 3 with life threatening consequences
aged 2 to 5 years	WHO Weight for height z score < 1 to 2	WHO Weight for height z score < 2 to 3	WHO Weight for height z score < 3	WHO Weight for height z score < 3 with life threatening consequences
aged <2 years	WHO Weight for length z score < 1 to 2	WHO Weight for length z score < 2 to 3	WHO Weight for length z score < 3	WHO Weight for length z score < 3 with life threatening consequences

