### **5.6.3.3. Vital Signs**

The following parameters measurements will be analyzed:

- Supine pulse rate (bpm)
- Supine systolic blood pressure (mmHg)
- Supine diastolic blood pressure (mmHg)

- Body temperature (°C)

The abnormalities in vital signs will be determined according to the criteria specified in the Cardiovascular Safety – Abnormalities Table (see Clinical Protocol Appendix 8).

An assessment is treatment-emergent if abnormality worsened as compared to the abnormality at baseline; this also includes the shift from abnormally high to abnormally low and vice-versa. Post-baseline abnormalities are always treatment-emergent with regard to missing abnormalities at baseline. The abnormally high values (i.e. abnormally high, grade 1 or mild, grade 2 or moderate, grade 3 or severe) versus the abnormally low values are considered equally important.

For each parameter, a “worst-case” analysis will be performed by using the worst abnormality and time point per participant. Worst-case will be derived within each analysis phase, including unscheduled assessments. In case the same participant has both abnormalities (low and high) for the same test within the same phase, the participant will be counted in the analysis for both abnormality directions (abnormally high and low).

Vital signs records with partial dates (any of day/month/year is missing) will not be used in the analysis but will be listed.

Descriptive statistics of continuous vital sign parameters and body temperature will be calculated for observed values and changes from baseline at each scheduled time point.

Shift tables will be provided summarizing the shift in vital sign and body temperature values from baseline over time with respect to abnormality criteria (low, normal, high) for each parameter by analysis phase.

A cross-tabulation of the worst abnormalities versus baseline per parameter and analysis phase will be presented including also the number of participants per abnormality, the number of participants with treatment emergent abnormalities per abnormality.

A tabulation of percentage and number of the participants who have treatment-emergent worst abnormalities per parameter and analysis phase will be included.

A listing including all parameters for participants with at least one treatment-emergent abnormality (on actual values or change from baseline) is provided. Additional vital signs assessments corresponding to the rash eCRF pages will be only listed as applicable.

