#### **5.7.7. Definition of Subgroups**

##### **5.7.7.1. Subgroups for Efficacy Analyses**

**Table 8: Subgroups for efficacy analyses**

Subgroup	Definition
Sex	Male, Female
Age	≤45 years, >45 years

Subgroup	Definition
Race	Asian, Non-Asian
Geographical Region	Europe (Spain, UK, Poland, Russia), Asia (South Korea, Japan, Taiwan, Hong Kong, Thailand), North America (US, Canada)
Type of NA at Baseline	TeD, TAF, ETV
HBsAg level at baseline	<100 IU/mL; ≥100 IU/mL-<1,000 IU/mL; ≥1,000 IU/mL-<10,000 IU/mL; ≥10,000 IU/mL
HBV RNA level at baseline	<1,000 copies/mL; ≥1,000 copies/mL
HBcrAg level at baseline	<3 log U/mL; ≥3 log U/mL-<4 log U/mL; ≥4 log U/mL
Anti-HBs level at baseline	<10 mIU/mL; ≥10 mIU/mL
Alanine Transferase (ALT) at baseline	≤1.0 ULN; >1.0 ULN
HBV Genotype	Genotype A, B, C, D, E, F, G, H, I, J and Unknown

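### The fever limit in the rash stopping rule (Protocol Appendix 6, Table 4) is printed as two different temperatures: 38°C is 100.4°F, not 100°F

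*Protocol*

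**What the plan says.** Table 4 in Protocol Appendix 6 (Section 10.6) sets out how rash is managed by grade. One route to Grade 3 is any cutaneous event together with one of four systemic features, and the second of these is "Fever >38°C or 100°F". The action for Grade 3 opens with "Must permanently discontinue JNJ-3989 and JNJ-6379", goes on to include PegIFN-α2a, and forbids rechallenge. The Grade 4 cell carries the same instruction. At Grades 1 and 2, by contrast, continuing treatment is left to the investigator.

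Protocol Section 7.1 makes the rule mandatory. Its list of discontinuation criteria includes a "Grade 3 rash (see Section 10.6, Appendix 6: Rash Management) or allergic reaction" at or above that grade.

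The protocol gives fever limits in both units in one other place, the DAIDS table in Appendix 9 (Section 10.9). Grade 1 fever there is "38.0°C to <38.6°C or 100.4°F to <101.5°F".

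SAP Section 5.3.2 counts a participant who discontinues treatment before Week 24 as a non-responder for the primary endpoint.

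**The concern.** The fever item is written as one threshold in two units, but the units do not agree. The rule it feeds is mandatory, permanent and binary, so its threshold should be one number. As printed, whether a participant with a rash and a borderline temperature loses JNJ-3989 and PegIFN-α2a for good can depend on which unit the site applies.

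The cost of the error is an unneeded permanent stop, and possibly different handling of the same temperature at different sites. If the stop comes before Week 24, the participant is also scored as a non-responder.

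**Working it through.** **Inputs**

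- Table 4, Grade 3 rash: 38°C and 100°F, offered as alternatives for one limit.
- Appendix 9, fever row, lower limits of Grades 1 to 4: 38.0°C/100.4°F, 38.6°C/101.5°F, 39.3°C/102.7°F and 40.0°C/104.0°F.
- Planned arm size: 34 (Protocol Section 4.1).

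**Step 1. Convert each limb of the Table 4 limit**

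- °F = °C × 9/5 + 32, so 38 × 9/5 + 32 = 100.4°F.
- °C = (°F − 32) × 5/9, so (100 − 32) × 5/9 = 37.78°C.

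The printed 100°F is not reproduced. It matches 38°C only if 37.78 is rounded to a whole degree Celsius, or 100.4 to a whole degree Fahrenheit.

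**Step 2. Size of the gap**

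- 100.4 − 100 = 0.4°F.
- 38 − 37.78 = 0.22°C.

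**Step 3. Check against the protocol's other fever scale**

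| Appendix 9, °C | Converted, °F | Printed, °F |
|---|---|---|
| 38.0 | 100.40 | 100.4 |
| 38.6 | 101.48 | 101.5 |
| 39.3 | 102.74 | 102.7 |
| 40.0 | 104.00 | 104.0 |

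All four pairs agree to the decimal place printed. The protocol therefore already contains the correct Fahrenheit equivalent of 38.0°C.

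**Step 4. A participant inside the gap**

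Take any rash with a temperature of 37.9°C: 37.9 × 9/5 + 32 = 100.22°F.

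- Fahrenheit limb: 100.22 is above 100, so the rash is Grade 3 and the stop is permanent.
- Celsius limb: 37.9 is not above 38, so this feature does not make the rash Grade 3.
- DAIDS fever row: 37.9°C is below the lower limit of Grade 1.

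The two limbs disagree for any reading above 100.0°F and up to 100.4°F (above 37.78°C and up to 38.0°C).

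**Step 5. What one such stop could do to the response rate**

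One participant in an arm of 34 is 1/34 = 2.9 percentage points of that arm's response rate. That is an upper limit per event, since the participant might not have responded anyway. It is not an estimate of what will happen.

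**The case against.** The best defence is that this is a rounding slip. Table 4 prints whole degrees, and 100.4°F does round to 100°F. The slip errs on the side of stopping, which is the cautious direction. Because the text says or, a stop at 100.2°F satisfies the rule as printed and would not be a protocol deviation. Section 7.1 also lets the investigator stop for safety or tolerability at any time. All of this stands and is why the severity is low. It does not rescue the entry: a rounded limit is acceptable in background text but not in a rule that removes treatment permanently.

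Four stronger readings are tempting and are not supported.

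- **That the protocol has two competing scales for stopping on rash.** A reader might infer this from the Note at the end of Section 7.1, "The grades are based on the DAIDS Toxicity Grading Scale", and from the mention of DAIDS in Section 8.3.7. The rash criterion itself names Appendix 6, Section 8.3.7.1 sends the reader to Table 4, and Appendix 9 gives DAIDS the role of adverse event reporting. Table 4 evidently governs stopping. That the two scales define Grade 3 differently follows from their different purposes.
- **That many participants will be caught.** Section 2.2.3.3 lists "alopecia, dermatitis, pruritis, dry skin, myalgia, arthralgia, asthenia, pyrexia, and fatigue" among PegIFN-α2a reactions seen in at least 10%, so a reader might expect rash with fever to be frequent. The list names dermatitis and pyrexia separately. It does not say how often they coincide, and it says nothing about a band 0.22°C wide.
- **That US sites will apply the lower limit.** SAP Table 8 includes the US among the regions, but neither document says which unit sites use to record temperature. SAP Section 5.6.3.3 analyses it in °C.
- **That the reference to JNJ-6379 affects someone.** The study interventions are JNJ-3989, an NA and PegIFN-α2a (Protocol Section 6.1). No participant receives JNJ-6379 in this study, so the text is a harmless leftover.

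**Conclusion.** Wrong as written, low severity. The two limbs of the fever limit differ by 0.4°F (0.22°C), and the Fahrenheit limb conflicts with the protocol's own DAIDS fever row. The finding rests only on unit conversion and on reading the °F figure as the intended equivalent of 38°C.

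Any practical effect depends on a rash coinciding with a temperature in the narrow band and on a site applying the °F figure. The documents give the frequency of neither, so the number affected cannot be derived. The direction is toward unneeded stopping. Through SAP Section 5.3.2 such a stop before Week 24 would count as non-response, but it does not follow that the primary test, the power or the sample size is compromised.

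**What to change.** In Table 4, Grade 3 rash, replace the fever item with **Fever >38.0°C (>100.4°F)**. This keeps the Celsius limit and brings the Fahrenheit figure into line with Appendix 9.

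In the same edit, delete JNJ-6379 from the action cells for Grade 3 and Grade 4. This is clerical.

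The cost is one number and one drug name in two cells at the next protocol amendment. No procedure, sample or analysis changes, and the SAP needs no edit.
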